8.1.1.2. Confirmatory Phase

The final hypothesis and endpoint measurements for the Confirmatory Phase are yet to be determined and will depend on the discoveries from Exploratory Phase data. However the primary objective of the confirmatory phase is to validate the accuracy of ¹⁸F-AV-1451 scans to predict clinically significant disease progression within 18 months from scan (e.g., cognitive function deterioration as measured by endpoints based on Exploratory Phase results). For the purpose of sample size calculation, we assumed that the target success criteria would be at least 70% sensitivity and at least 70% specificity for ¹⁸F-AV-1451 scans to detect this deterioration, with the lower bound of 95% confidence intervals (CI) above 50% for both sensitivity and specificity. Preliminary analysis of the exploratory phase cohort data showed that clinical assessments may have a relatively large variance. It is important to ensure that enough subjects will be in each group for sensitivity and specificity calculation (i.e., the subjects with or without a significant disease progression). To that end, we assume at least 20% of the subjects will be in each group at the 18 month follow up. With this assumption, a 5% two-sided type I error rate,

and that 95% CI will be calculated using Wilson score method, a sample of 115 subjects will provide an over 90% probability to observe lower bound of 95% CI above 50%, for both sensitivity and specificity. Also assuming an approximate 20% drop out rate over the 18 months follow up, this study will aim to enroll 150 subjects in total.

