4.5 Determination of Sample Size

A total of 230 subjects (80 cognitively healthy volunteers, 80 MCI and 70 AD) will be enrolled in the Exploratory Phase of this study. To explore the Flortaucipir SUVR values across age strata among cognitively healthy subjects, these subjects will be divided into 5 age groups as 20-40 years old, 50-59 years old, 60-69 years old, 70-79 years old and 80 years old or above. There will be 15 subjects in each of the 50 or older age groups and about 20 subjects from age group 20-40 years old. From a preliminary analysis of study T807000, the standard deviation (SD) of SUVR from combination region of interest (ROI) was 0.06 for subjects with low probability of AD. Therefore assuming a 0.06 SD, a sample of 15 subjects will give an approximately 90% probability to observe a 95% confidence interval as accurate as +/-0.04 around the point estimation.

From previous studies, the amyloid positive rate is approximately 50% among MCI patients and approximately 80% from AD subjects. Therefore 80 MCIs and 70 ADs will likely result in 40 amyloid positive MCIs and 56 amyloid positive ADs. Also from study T807000, the combination ROI SUVR difference between CN and AD was 0.39, with a pooled SD of 0.27. Assume a pooled SD of 0.30, a sample of 60 CNs and 56 amyloid positive ADs will give a 90% power to detect a 0.18 difference between the CN and AD groups.

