All values will be summarized by the four diagnostic groups: young cognitively normal (YCN) subjects (healthy volunteers ≥ 20 years of age and ≤ 40 years of age), old cognitively normal (OCN) subjects (healthy volunteers ≥ 50 years of age), patients with AD, patients with MCI, and overall. Frequency distributions including counts and percentages will be included for all categorical outcomes. Summary statistics including mean, standard deviation, median, minimum and maximum values will be presented for all continuous outcomes. Unless otherwise specified, hypothesis testing will be two-sided with type I error rate of 0.05.

All statistical analyses will be performed using SAS® version 9.3 or higher.

7.2 **Adjustments for Covariates**

Not applicable for the primary analyses.

7.3 **Handling of Dropouts or Missing Data**

Dropout subjects will not be replaced in this study. For situations with no rules for handling missing data, the default will be no imputation.

A likelihood-based mixed effects model for repeated measures will be used to handle missing longitudinal follow up cognitive measurements, or flortaucipir SUVr data. The model parameters are simultaneously estimated using restricted likelihood estimation incorporating all of the observed data. Estimates have been shown to be unbiased when the missing data are missing at random and when there is ignorable non-random missing data.

Repeated measures analyses will only use data from visits where the data was scheduled to be collected. When subjects discontinue from the study early, there may be efficacy data measurements at visits where the variables were not scheduled to be collected. These data will appear in listings only.

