8.6.1.3.3 Multi-variate models to explore possible factors for cognitive impairments

To further explore the possible factors for cognitive impairment, multivariate models will be conducted. The following variables will be used as dependent variables for each of these models: ADAS Cog 11, MMSE, and FAQ. Each of these models will include these variables as independent variables: baseline age, ANART, MUBADA SUV_r, florbetapir SUV_r, whole brain volume, and ApoE E4 status. Stepwise selection technique will be used to build the most parsimonious model, with entry and stay selection p-value set at 0.2. The analyses will be run separately with all subjects except for YCN, and with AB+ subjects only.

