The analysis will be completed for AB+ subjects. A multivariate step wise selection regression model will be used to explore factors associated with the change in Flortaucipir SUVr (MUBADA). The dependent variable will be Flortaucipir SUVr (MUBADA) change at 18 months. The independent variables include baseline information such as age, cognitive assessments (MMSE), APOE4 status (carrier or non-carrier), florbetapir SUVr, and flortaucipir MUBADA SUVr. The significance level of entry and stay in the model will be both set as 0.2. For each variable in the final model, the parameter estimate, SE, 95% CI and associated p-value will be reported.

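### SAP 8.6.2.1 and 8.6.2.4.5 report ordinary 95% CIs and p-values after stepwise selection at 0.2; for null or weak factors that are retained, those intervals undercover

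*SAP*

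**What the plan says.** SAP 8.6.2.1, in the part on factors associated with flortaucipir SUVr change, fits a stepwise regression in amyloid-positive subjects with 18-month MUBADA SUVr change as the outcome. The rule is: "The significance level of entry and stay in the model will be both set as 0.2". The reporting is: "For each variable in the final model, the parameter estimate, SE, 95% CI and associated p-value will be reported". The candidates are given as: "The independent variables include baseline information such as age, cognitive assessments (MMSE), APOE4 status (carrier or non-carrier), florbetapir SUVr, and flortaucipir MUBADA SUVr". That names five variables, but the words *such as* leave the list open.

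SAP 8.6.2.4.5 repeats the selection rule and the reporting sentence for 18-month change in ADAS-Cog 11, MMSE and FAQ, also in amyloid-positive subjects. It names six candidates, again with an open list: the matching baseline score, age, ANART, APOE4 status, florbetapir SUVr and MUBADA SUVr.

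SAP 8.6.1.3.3 (cross-sectional models) uses the same 0.2 threshold: "Stepwise selection technique will be used to build the most parsimonious model". Its list of six is closed, and it does not say that CIs or p-values will be reported.

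SAP 7.1 sets the general rule that "hypothesis testing will be two-sided with type I error rate of 0.05". SAP 7.6 deals only with multiplicity across diagnostic groups. Neither document describes a selection adjustment, bootstrap, shrinkage, full-model table or caveat for the stepwise models.

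**The concern.** A standard 95% CI assumes that the model was fixed before the data were seen. Here a variable reaches the table only if its p-value is below 0.2, and only the survivors are shown. Conditioning on survival does two things. Mainly, it selects estimates that happen to lie away from zero. To a lesser degree, it leaves SEs smaller than those of the full model. A reader of the table has no way to undo either effect.

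What is at stake is how these tables are read. A factor with no relation to tau accumulation or decline may appear with a p-value below 0.05, and a weak relation may appear about twice its true size. Calling the analysis exploratory excuses unadjusted multiplicity and tentative conclusions. It does not make an interval labelled 95% cover 95%.

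**Working it through.** **Sample size.** The SAP gives no power or sample size for these models. The nearest figure, in SAP 4.5, is "80 MCIs and 70 ADs will likely result in 40 amyloid positive MCIs and 56 amyloid positive ADs". It reproduces: 80 × 0.50 = 40, 70 × 0.80 = 56, and 40 + 56 = 96. Both models need 18-month data. The only dropout figure is in Protocol 8.1.1.2, for the confirmatory phase: "assuming an approximate 20% drop out rate over the 18 months follow up". Borrowing it as an assumption gives 96 × 0.8 = 76.8, about 77. Amyloid-positive healthy older subjects could add to this, but their number is not given.

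**Analytic result, one null factor, uncorrelated candidates.** Under the null, p is uniform, so

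- P(p<0.05 given p<0.2) = 0.05 / 0.20 = 25%.
- For a null factor the 95% CI misses the truth exactly when p<0.05, so coverage given retention = 1 − 0.25 = 75%.
- P(at least one of five independent null factors retained) = 1 − 0.8⁵ = 67%; for six, 1 − 0.8⁶ = 74%.

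These figures follow from the SAP's thresholds and do not depend on n.

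**Simulation, all five candidates null.** Forward-backward stepwise least squares, entry and stay 0.2, 2,000 runs per setting, equal pairwise correlation (assumed), ordinary t-based 95% CIs from the final model:

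| n | Correlation | Coverage, retained factors | At least one null retained | At least one null shown with p<0.05 |
|---|---|---|---|---|
| 77 | 0 | 72% | 67% | 25% |
| 77 | 0.3 | 65% | 65% | 29% |
| 77 | 0.5 | 57% | 59% | 31% |
| 96 | 0 | 74% | 67% | 22% |
| 96 | 0.3 | 67% | 63% | 27% |
| 96 | 0.5 | 56% | 58% | 31% |

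For comparison, the model that keeps all five candidates covered about 94% to 96%. Over n = 60 to 96, final-model SEs were about 3–4%, 9–11% and 15–18% below full-model SEs at correlations 0, 0.3 and 0.5. At zero correlation, then, the undercoverage is almost entirely due to selection of the estimate.

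**Simulation, mixed effects.** n = 77, true slopes 0.5, 0.3, 0.1, 0, 0 in residual-SD units:

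| Slope | Coverage when retained, correlation 0 | Correlation 0.3 |
|---|---|---|
| 0.5 | 95% | 94% |
| 0.3 | 97% | 97% |
| 0.1 | 90% | 86% |
| 0 (two factors) | 73%, 75% | 69%, 72% |

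The 0.1 slope was retained in 33% and 31% of runs. When retained, its mean absolute estimate was 0.22 and 0.25. Further runs at n = 77 and 96 put the retained weak effect at about 0.21 to 0.25. Taking null and mixed settings together, coverage of a retained null factor at correlation 0.3 is about 62% to 74%. With roughly 400 retentions per factor, the simulation error on one such figure is about √(0.65 × 0.35 / 400) = 2.4 percentage points.

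**Is zero correlation plausible?** SAP 4.2 looks for higher uptake with greater cognitive impairment, and 8.6.2.1 lists both MMSE and baseline MUBADA SUVr as candidates. Some correlation should be expected, though the documents give no value.

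**Is selection needed?** Subjects per named candidate: 77 / 6 = 12.8 at the low end and 96 / 5 = 19.2 at the high end. A full linear model is feasible.

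**The case against.** The strongest reply is that these models are exploratory, carry no decision rule and use a pre-specified liberal threshold. Their stated aim is to explore associated factors, and the primary longitudinal estimate comes from a separate mixed model with fixed covariates. All of that is correct and limits the severity. It does not repair the intervals.

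A second reply is that the error is conditional on retention. This is also correct: over all runs, a given null factor reached p<0.05 in only about 5% to 9%. But the table shows only retained factors, so the conditional figure is the one that applies to what is read.

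Four stronger readings are tempting, and the documents do not support them:

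- *All three stepwise sections report post-selection intervals.* SAP 8.6.1.3.3 shares the selection rule but states no CI or p-value reporting.
- *The models feed the confirmatory hypotheses.* The 8.6.2.1 outcome is SUVr change, and the protocol plans no follow-up PET in the confirmatory cohort, so it cannot be tested there. The SAP also lists the analyses to be repeated at baseline MMSE 20–27, the population resembling that cohort, and the stepwise models are not among them. The protocol's general statement about imaging and cognitive change leaves room for 8.6.2.4.5 to contribute a lead, but no more, and that lead would be tested in separate subjects.
- *Every retained factor has too narrow an interval.* Strong factors keep about nominal coverage.
- *The fault is chiefly in the SEs.* Most of it comes from estimates selected away from zero.

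**Conclusion.** The point holds for SAP 8.6.2.1 and 8.6.2.4.5. Intervals and p-values reported after selection at 0.2 are not what their labels say for null or weak factors that survive. The 75% coverage and 25% chance of p<0.05 for a retained null factor rest only on the SAP's thresholds and on uncorrelated candidates; correlation lowers the coverage further. The simulated figures rest on assumed effects, assumed equal correlations and an assumed n of about 77 to 96, the lower value using a dropout rate that the protocol states for the other phase. That the CIs are unadjusted is inferred from the absence of any adjustment in the documents.

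Severity is low to moderate: no primary estimate changes, but the correction is nearly free.

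**What to change.** In SAP 8.6.2.1 and 8.6.2.4.5:

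1. Delete *such as* and close the candidate lists at the five and six baseline variables already named.
2. Fit that full model and report every coefficient with its 95% CI, whether or not it is significant.
3. If stepwise selection is kept, present the selected set as a descriptive supplement, without CIs or p-values.

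The same change is advisable in 8.6.1.3.3 for consistency only; its list is already closed.

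The cost is SAP wording and slightly wider intervals. No additional data are needed.

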8.6.2.2 Analysis of Second Efficacy Variable

Not applicable for this section to this study.

8.6.2.3 Analysis of additional Efficacy Variable

Not applicable to longitudinal part of this study.

8.6.2.4 Exploratory Analyses

8.6.2.4.1 Mixed Model Repeated Measures for Comparison of Psychometric Assessment over time between diagnostic groups

Descriptive summary statistics for each cognitive scale (ADAS, MMSE, FAQ, and ADAS+FAQ composite) at baseline, 9 month, and 18 month will be summarized by subjects' tau and/or amyloid status of interest (details below). The change from baseline to 9 month and 18 month will be summarized in the same corresponding table.

Change from baseline for each psychometric assessment will be analyzed using mixed model with repeated measures (MMRM) for subjects who have follow-up information for 18 months (baseline, 9 months, and/or 18 month).

The MMRM model will be run to include MCI/AD subjects with these tau and/or amyloid status classified as below respectively:

- 1: Tau visual reads as AD++ vs. non-AD++ ;
- 2: Three level categorical variable by combining tau and amyloid status:
 - a. AB+ AD++ (AB+ and tau pattern likely to progress)
 - b. AB+ non-AD++ (AB+ and tau AD pattern but not likely to progress, i.e., AB+ AD+ subjects but not AD++, or AB+ AD-)
 - c. AB-

For this analysis, time will be considered to be Categorical variable. A mixed model will be used with psychometric score change at each visit as dependent variable. Independent variables include categorical variable baseline tau (AD++ vs non-AD++) and/or amyloid status by visual interpretation (category a, b, c defined above in this section), visit and interaction of tau status and visit, and baseline age, ANART score and psychometric score as continuous covariates. In order to appropriately model the within subject covariance, the covariance structure must be pre-specified. Each model should be fit using the unstructured covariance structure. If this structure does not converge, then covariance structure in the order of the auto-regressive, and toeplitz structures and the compound symmetry will be used.

The least squares (LS) mean from the model will be displayed separately for each Tau status and/ amyloid status by visual interpretation with the corresponding 95% confidence intervals and p-values testing that the LS mean is significantly different between any of the two categories.

In addition, LS means difference between any of the two categories will be presented with the 95% confidence interval and p-value testing that the difference is significantly different than zero. The Kenward-Roger approximation will be used to estimate denominator degrees of freedom.

The LS means at each visit from the models described above will be displayed by line graphs, by the tau and/or amyloid status.

CDR-SB scales were only collected at 9 and 18 months. Thus an ANCOVA model will be applied to explore the relationship between CDR-SB change and baseline tau/amyloid status. The model will use CDR-SB change from 9 month as dependent variable, and independent variable will include categorical variable baseline tau and/or amyloid status by visual interpretation (as described above), and continuous covariates including baseline age, ANART score and psychometric score. LS means and difference in LS means for the tau/amyloid status will be calculated through proper contrast.

To visually display the change of cognition/function assessments by subjects' tau status, the follow plots will be made: cumulative frequency of each score change at 18 months as y-axis, score change at 18 months as x-axis. The data points should be connected, and

displayed according to tau status (AD++ vs. non-AD++, or AB+AD++, AB+ non-AD++, and AB-). The plots will be completed for ADAS-Cog 11, MMSE, FAQ, ADAS+FAQ and CDR.

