2 INTRODUCTION

Molecular imaging biomarkers have the potential to aid in the diagnosis of patients with cognitive impairment who are being evaluated for Alzheimer's disease (AD) (Dubois, 2010; McKhann, 2011). Positron emission tomography (PET) ligands such as florbetapir F 18 (Wong, 2010) may provide a minimally invasive estimate of cortical beta amyloid (AB) neuritic plaque deposition, a hallmark pathology, and a required element for the evaluation of AD neuropathologic diagnosis (Hyman, 2012). Multiple studies comparing amyloid PET scans to histopathologic assessment of amyloid burden, in subjects for whom biopsy samples were available or who came to autopsy after receiving a PET amyloid scan, support the relationship between PET amyloid imaging results and cortical neuritic plaque density (Clark, 2011, 2012; Leinonen, 2008; Sojkova, 2011; Kantarci, 2011; Burack, 2010). The largest of these studies (Clark, 2012) demonstrated a high sensitivity and specificity for florbetapir PET to discriminate subjects with subsequent autopsy findings of no or sparse neuritic plaques (amyloid negative) from those with moderate to frequent plaques (amyloid positive).

The ability to image brain amyloid with compounds such as florbetapir is an important advance for diagnosis of neurological disease. An amyloid negative florbetapir PET scan indicates the absence of a hallmark pathology and is inconsistent with a diagnosis of AD. However, because amyloid is believed to accumulate very early in the disease process (Jack et al., 2010) and may be present in other diseases or in clinically normal elderly subjects (Sperling et al. 2011; Price and Morris, 1999), the density or distribution of amyloid in subjects with a positive scan is not associated with Alzheimer's disease severity, has not been established to predict rate of future deterioration and has not been established as a tool to predict or monitor response to therapy.

In contrast to AB neuritic plaques, the density and distribution of phosphorylated tau, aggregated in neurofibrillary tangles, increases with AD-related cognitive impairment and correlates with neurodegeneration (Dickson et al., 1997; Duyckaerts et al., 1987). Thus, a PET imaging agent that binds to phosphorylated tau has potential application as a biomarker for disease severity/neurodegeneration and may be useful both for selecting patients for therapy and for monitoring disease progression in therapeutic trials.

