4 STUDY DESIGN

4.1 General Design

This study is an open label, multicenter Phase 2 study. This study is conducted in two phases, an exploratory (first) phase and complimentary (second) phase. The study will enroll cognitively healthy volunteers, subjects with mild cognitive impairment (MCI) and subjects with Alzheimer's disease. Approximately 230 subjects will be enrolled in the study: 80 cognitively healthy volunteers (20 subjects who will be ≥ 20 to ≤ 40 years of age, and 60 subjects who will be ≥ 50 years of age), 80 subjects with MCI, 70 subjects with AD (60 subjects with a Mini-Mental State Examination (MMSE) ≥ 20 , and 10 subjects with an MMSE > 10 and < 20). For the 60 cognitively healthy volunteers ≥ 50 years of age, these subjects will be distributed across age deciles (50-59, 60-69, 70-79 and > 80).

All subjects will provide informed consent before starting any study procedures.

Screening assessments may take place over several days and will include demographic information, cognitive testing, safety assessment, and MRI, including both volumetric and standard clinical sequences. Subjects who qualify for the study will undergo both a florbetapir F 18 PET imaging session and a Flortaucipir PET imaging session. The imaging sessions must be performed at least 48 hours apart, but not more than 60 days apart. The order of the scans is interchangeable. Some subjects, who are ≥ 50 years of age, will have the option to also participate in cerebrospinal fluid (CSF) collection by lumbar puncture (LP).

Subjects who are ≥ 50 years of age will return for have a follow-up visits at 9 (+/-2) months 18 (+/-2) following the initial Flortaucipir scan. Cognitive assessments and updates to concomitant medications and medical history will be collected at each follow-up visit. Subjects will also have follow-up Flortaucipir scans and MRI, including both volumetric and

standard clinical sequences. A sub-set of subjects may have the option to have an additional resting state functional (rsf) MRI sequence scan in addition to the volumetric and standard clinical sequences at both the screening MRI and follow-up MRIs. Subjects or their designated decision maker will be contacted by phone at 5 and 14 months following the initial Flortaucipir scan to collect updated concomitant medications and medical history.

Florbetapir F 18 PET Imaging Session:

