6.4.1.2 Qualitative assessment for Flortaucipir and Diagnostic Performance

At the exploratory phase, the baseline flortaucipir scan images will be visually interpreted by Avid's imaging experts. The scans will be classified as either

- AD pattern (AD+)
- AD pattern and likely to progress (AD++)
- Not consistent with an AD pattern (AD-)

AD++ also is referenced as Tau+ in the SAP, and the rest is referenced as Tau-.

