8.6.2.4.2 Rate Ratio of Clinically Meaningful Changes by Baseline Tau Scan Status

The analyses for clinically meaningful changes will be restricted to AD/MCI subjects only.

Clinically meaningful changes assessed by psychometric scores are defined in section 6.4.2.3.1

For each of the categorized clinically meaningful changes (event) except for CDR global score change, a Poisson regression model will be applied. The model will have these defined event as dependent variable respectively, and the independent variables will include tau status at baseline (AD++ vs. non-AD++), visit and the interaction of tau status and visit as a categorical variable, and continuous covariates that include baseline psychometric score, age, and ANART.

At each visit, person-year will be calculated for each subjects, as time from baseline to first event, or time from baseline to visit date or end of study if no event for the subject.

General estimating equation (GEE) technique will be used to adjust for the intra subject correlation. The variance-covariance matrix is pre-specified: each model should be fit using the unstructured covariance structure. If this structure does not converge, the exchangeable, auto-regressive, and m-dependent structures will be fit and the model with the lowest BIC value will be selected to use. The rate ratio estimated at 18 month visit will be reported along with 95% confidence interval.

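### The cognition MMRM fixes one baseline-score slope for both visits, so the 18-month tau difference can absorb part of a baseline severity gap; add baseline score × visit

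*SAP*

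**What the plan says.** SAP 8.6.2.4.1 fits a mixed model to each cognitive or functional scale, with "psychometric score change at each visit as dependent variable". On the analysis set: "The MMRM model will be run to include MCI/AD subjects". SAP 4.1 plans "80 subjects with MCI, 70 subjects with AD", so 150 in all. On the within-subject covariance: "Each model should be fit using the unstructured covariance structure"; simpler structures are used only if it fails to converge.

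The fixed effects are tau status (or a three-level tau/amyloid category), then "visit and interaction of tau status and visit, and baseline age, ANART score and psychometric score as continuous covariates". No product of baseline score and visit is listed. LS means are compared between categories and plotted by visit.

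Tau status is the baseline visual read of SAP 6.4.1.2: AD++ against the rest. SAP 2 says that the density and distribution of tau "increases with AD-related cognitive impairment and correlates with neurodegeneration".

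The Poisson GEE of SAP 8.6.2.4.2 has a similar list, "visit and the interaction of tau status and visit as a categorical variable, and continuous covariates that include baseline psychometric score, age, and ANART", and reports the 18-month rate ratio.

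**The concern.** In a randomised comparison, a common baseline slope across visits would do little harm to the group contrast, because the groups have the same expected baseline. Here the groups are observed. By the SAP's own reasoning, AD++ subjects are likely to be more impaired at entry. Diagnosis (MCI or AD) is not a covariate in this model, so baseline score carries most of the severity adjustment.

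The outcome is change from baseline. If more impaired subjects decline faster, the effect of baseline score on change builds up over time. Under linear decline the 18-month slope would be 18/9 = 2 times the 9-month slope. A model that allows only one slope then corrects too little at 18 months, and the uncorrected part has nowhere to go except the tau × visit term. The SAP's 18-month tau difference in cognition could look larger than it is.

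**Working it through.** The documents state no power, sample size or effect size for this model, so there is no planned figure to reproduce. The check asks how large the leak could be.

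**Inputs from the documents.** 150 MCI/AD subjects (SAP 4.1); visits at 9 and 18 months; two-sided 5% tests (SAP 7.1); a 4-point ADAS-Cog 11 change as the clinically meaningful threshold (SAP 6.4.2.3.1). The 20% missing at 18 months is borrowed from the confirmatory-phase dropout in Protocol 8.1.1.2.

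**Inputs assumed (ADAS-Cog 11).** Baseline difference between tau groups D = 3 to 6 points; baseline SD 6; 35% AD++; residual SD s9 = 5 at 9 months and s18 = 5 to 8 at 18 months; correlation ρ = 0.4 to 0.75; slopes β9 and β18 of change on baseline score, with β18 above β9 by 0.10 to 0.20.

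**Formula (complete data, large sample).** With tau × visit free and one baseline slope b, generalised least squares gives

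- w = (s9² − ρ·s9·s18) / (s9² + s18² − 2ρ·s9·s18), the weight on the 18-month slope;
- b = β9 + w(β18 − β9);
- bias in the 18-month tau effect = (β18 − b) × D.

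**Worked case.** s9 = 5, s18 = 6.5, ρ = 0.6, slopes 0.15/0.30, D = 6:

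- w = (25 − 19.5)/(25 + 42.25 − 39) = 5.5/28.25 = 0.195
- b = 0.15 + 0.195 × 0.15 = 0.179
- 18-month bias = (0.30 − 0.179) × 6 ≈ 0.72 points
- 9-month bias = (0.15 − 0.179) × 6 ≈ −0.18 points

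**Range over the grid.**

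| Slopes 9/18 | s18 | ρ | D | w | b | 18-month bias |
|---|---|---|---|---|---|---|
| 0.10/0.20 | 5 | 0.4 to 0.75 | 3 | 0.50 | 0.150 | 0.15 |
| 0.15/0.30 | 6.5 | 0.6 | 6 | 0.19 | 0.179 | 0.72 |
| 0.10/0.30 | 6.5 | 0.6 | 6 | 0.19 | 0.139 | 0.97 |
| 0.10/0.30 | 8 | 0.75 | 6 | −0.17 | 0.066 | 1.41 |

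The leak is 0.15/3 = 5% to 1.41/6 = 23% of the baseline difference, and 4% to 35% of the 4-point threshold.

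**Simulation.** Unstructured covariance, 150 subjects, 35% AD++, SDs 5/6.5, ρ = 0.6, 20% missing at 18 months, 600 runs per row. Entries are the mean 18-month tau effect and the rejection rate. The Monte Carlo error of a 5% rate is √(0.05 × 0.95/600) ≈ 0.9 percentage points.

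| Slopes 9/18 | D | True effect | Planned model | With baseline × visit |
|---|---|---|---|---|
| 0.15/0.15 | 6 | 0 | −0.06 (5.8%) | −0.09 (5.2%) |
| 0.15/0.30 | 0 | 0 | 0.08 (4.7%) | 0.08 (4.3%) |
| 0.15/0.30 | 3 | 0 | 0.32 (4.5%) | −0.06 (4.7%) |
| 0.10/0.20 | 6 | 0 | 0.54 (9.0%) | 0.02 (5.3%) |
| 0.15/0.30 | 6 | 0 | 0.79 (10.0%) | 0.04 (6.0%) |
| 0.10/0.30 | 6 | 0 | 1.03 (14.3%) | −0.01 (5.0%) |
| 0.20/0.40 | 6 | 0 | 1.10 (12.2%) | 0.09 (4.5%) |
| 0.15/0.30 | 6 | 3.0 | 3.78 (81.5%) | 3.02 (57.2%) |

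A second simulation with SDs 4.5/6.5, ρ = 0.6 and D = 6 gave a spurious effect of 0.56 to 1.17 points and 8% to 15% rejection. Baseline × visit removed it for about 3% to 5% more standard error.

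**Cost in precision, worked case, complete data.** The two groups contribute 42.25/(150 × 0.35 × 0.65) = 1.238 to the variance of the 18-month contrast. A separate 18-month slope adds 36 × 42.25/(150 × 36) = 0.282. The common slope adds 36 × [25 × 42.25 × 0.64/28.25]/(150 × 36) = 0.160. The standard error ratio is √(1.520/1.398) = 1.043. In the last row of the grid table the same arithmetic gives √(2.302/2.036) = 1.063.

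**The case against.** A reader might infer that the 18-month tau effect absorbs the whole baseline severity difference. It does not. Baseline score is in the model, and only the gap between the 18-month slope and the common slope leaks: 5% to 23% of the baseline difference in the range above. With equal slopes or balanced groups nothing leaks, and at D = 3 with slopes 0.15/0.30 the rejection rate stayed at 4.5%.

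The documents give no slopes, SDs, correlation or baseline difference by tau group. They support a severity gap between tau groups, but say nothing about slopes growing with time. Nor does the common slope always sit at the 9-month value: w runs from −0.17 to 0.50. This objection stands as a limit on the size, not on the mechanism.

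A reader might also infer that this contrast is the result that generates the confirmatory hypothesis. Protocol 8.1.4 draws hypotheses from several imaging parameters and assessments. Protocol 8.1.1.2 sizes the confirmatory phase on sensitivity and specificity, for which the closer exploratory analysis is the 2×2 table of SAP 8.6.2.4.4. The confirmatory phase uses separate subjects. SAP 8.6.2.4.1 also does not say that the tested LS-mean difference is the one at 18 months; only the line graphs are explicitly by visit. Averaged over visits, the worked case leaks (0.72 − 0.18)/2 = 0.27 points.

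Finally, a reader might carry the bias over to the Poisson GEE. That has not been shown. The model works with person-years, and a constant effect of baseline score on the log rate already lets its effect on cumulative events grow with follow-up. Nor has any age or ANART imbalance been shown to matter.

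The plan has partial safeguards: scores summarised by tau status and visit, a repeat in subjects with MMSE 20 to 27, and the 18-month regression of SAP 8.6.2.4.5. The summaries would expose an imbalance without correcting for it. The repeat narrows the severity range but keeps the same model. The regression has its own baseline slope, but covers only amyloid-positive subjects, uses stepwise selection, and takes SUVr in place of the AD++ read.

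**Conclusion.** The point holds conditionally. It is certain from the text that the model has one baseline-score slope for two visits and tau groups that were not randomised. If baseline severity predicts change more strongly at 18 months and AD++ subjects start worse, the 18-month tau difference is inflated. For ADAS-Cog 11 the inflation is roughly 0.15 to 1.4 points, with type I error from nominal to about 15%. Every input to that range other than the sample size, visits and test level is an assumption or borrowed. In an exploratory analysis this is a worthwhile, cheap improvement and does not invalidate the plan.

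**What to change.** In SAP 8.6.2.4.1, add baseline psychometric score × visit to the fixed effects, and carry it into the repeat in subjects with MMSE 20 to 27. It adds one parameter per model and one line of SAP text. The standard error of the 18-month contrast rises by about 5% at most in the simulated settings, and by about 6% at the extreme corner of the grid. If the slopes turn out equal, that small loss is the whole cost.

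Age × visit and ANART × visit in the MMRM, and covariate × visit terms in the Poisson GEE of SAP 8.6.2.4.2, can be listed as optional sensitivity analyses.
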